#### **7.1.4.3 Between days 14-21 cycle 1**

- Repeat biopsy in selected cases.

#### **7.1.4.4 Every 3 cycles between day 15 and 21 (C3D15-D21, C6D15-21, etc)**

- Repeat cross sectional imaging (CT or MRI)

#### **7.1.4.5 End of treatment visit**

- Record concomitant medications
  - Vitals (temperature, HR, BP and RR)
  - History and physical exam
  - ECOG performance status
  - Toxicity assessment
    - Laboratory Assessments
      - Hematology hemoglobin, hematocrit, red blood cell count, white blood cell count with differential and platelet count
      - Chemistry sodium, potassium, chloride, bicarbonate, magnesium, calcium, phosphorus, blood urea nitrogen, creatinine, glucose (random), total bilirubin, LDH, total protein, ALP, ALT, AST, and albumin
      - Tumor markers - when applicable
      - T3, FT4, TSH cycle 2 and then after every 3 cycle
- Blood sample 20 cc for correlative work

#### **7.1.5 Safety Follow-Up Visit**

The mandatory Safety Follow-Up Visit should be conducted approximately 30 days after the last dose of trial treatment or before the initiation of a new anti-cancer treatment, whichever comes first. All AEs that occur prior to the Safety Follow-Up Visit should be recorded. Subjects with an AE of Grade > 1 will be followed until the resolution of the AE to Grade 0-1 or until the beginning of a new anti-neoplastic therapy, whichever occurs first. SAEs that occur within 90 days of the end of treatment or before initiation of a new anti-cancer treatment should also be followed and recorded. Subjects who are eligible for retreatment with pembrolizumab/XL888 (as described in Section 7.1.6.2) may have up to two safety follow-up visits, one after the Treatment Period and one after the Second Course Phase.

### **7.1.6 Follow-up Visits**

Subjects who discontinue trial treatment for a reason other than disease progression will move into the Follow-Up Phase and should be assessed every 6 weeks ( $42 \pm 7$  days) by radiologic imaging to monitor disease status. After 1 year, the imaging time point will occur every 9 weeks ( $\pm 7$  days). Every effort should be made to collect information regarding disease status until the start of new anti-neoplastic therapy, disease progression, death, end of the study or if the subject begins retreatment with pembrolizumab/ XL888 as detailed in Section 7.1.6.2. Information regarding post-study anti-neoplastic treatment will be collected if new treatment is initiated.

Subjects who are eligible to receive retreatment with pembrolizumab/ XL888 according to the criteria in Section 7.1.6.2 will move from the follow-up phase to the Second Course Phase when they experience disease progression. Details are provided in Section 6.2 – Trial Flow Chart for Retreatment.

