### **5.7.2 Subject Replacement Strategy**

Patients who do not complete the intended course of chemotherapy due to reasons other than toxicity will be considered as in-evaluable for the primary endpoint and will be replaced.

[illegible]

Trial Period:	Treatment Cycles a									End of Treatment	Post-Treatment		
Treatment Cycle/Title:	Main Study Screening (Visit 2)	1	2	3	4	5	To be repeated beyond 8 cycles			Discon	Safety Follow-up	Follow Up Visits b	Survival Follow-Up
Scheduling Window (Days):	-28 to -1	± 3	± 3	± 3	± 3	± 3	± 3	± 3	± 3	At time of Discon	30 days post discon ± 7 days	Every 8 weeks post discon	Every 12 weeks
Comprehensive Serum Chemistry Panel	X	X	X	X	X	X	X	X	X	X	X	X	
Fasting triglyceride, cholesterol and glucose	X			X				X					
Urinalysis	X			X				X		X			
T3, FT4 and TSH	X		X			X			X	X	X		
ECG g	X	X	X		X		X g		X g				
Tumor Imaging	X f			X h			X h						
Archival or Newly Obtained Tissue Collection i	X	X											
Correlative Studies Blood Collection j	X	X	X	X						X			

- Treatment cycles are 3 weeks
- Only for patients with ongoing treatment related toxicities
- Pembrolizumab will be given day 1, XL888 twice weekly orally
- ECOG performance status should be done within 10 days or less from day 1 of cycle 1
- Ophthalmologic exam done at baseline and repeated only if there are symptoms
- Baseline imaging with 8 weeks of day 1 is acceptable
- ECG day1 2 to 3 hours after administration of XL888 every other cycle after C2 (C1, C2, C4, C6 etc)
- Scans will be done every 3 cycles between day 15 and day 21
- Paired biopsies will only be obtained from 16 patients on the dose expansion cohort
- Samples will be collected at baseline, day 15, and every cycle for the first 9 weeks. Analysis will include proportion of T, B, NK, memory and effector T cell subsets and expression of PD-1, PD-L1 and B7 family members. Samples will be collected at baseline and on weeks 6 and 9. This will be performed using interferon- gamma and CD107.

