### **8.3 Statistical and Analytical Plans**

Summary statistics will be presented for all safety, efficacy and biomarker parameter analyses. The purpose of these analyses is hypothesis generating and therefore, formal statistical testing will not be performed. Various exploratory statistical tests may be applied to data generated from this trial to generate hypotheses to be tested in subsequent trials. In general, data for continuous parameters will be presented using descriptive statistics including sample size, mean, and median; standard deviation; and minimum and maximum. Categorical parameters (such as pathologic response rate) will be displayed using counts and percentages. Toxicities will be presented as worst toxicity per patient and will be reported as percent toxicity.

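### Sections 5.7, 6.1 and 7.1.6 conflict on disease follow-up after treatment stops without progression, so PFS and response duration can be censored early or dated late

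*Combined protocol and SAP*

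**What the plan says.** **Section 7.1.6 (Follow-up Visits).** A patient who stops for any reason other than progression "will move into the Follow-Up Phase and should be assessed every 6 weeks" (42 ± 7 days), by radiologic imaging. The interval then lengthens: "After 1 year, the imaging time point will occur every 9 weeks".

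**Section 5.7 (Withdrawal/Discontinuation).** The same patients are followed for disease status until progression, non-study cancer treatment, withdrawal of consent or loss to follow-up. No interval is given. The section refers to Section 6 and to the visit requirements for the follow-up procedures.

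**Section 6.1 (Study Flow Chart).** The follow-up column is headed "Every 8 weeks post discon". Its footnote reads "Only for patients with ongoing treatment related toxicities". The "Tumor Imaging" row is marked at screening and at two on-treatment points, and is blank in every post-treatment column.

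**On treatment.** The chart states "Treatment cycles are 3 weeks" and "Scans will be done every 3 cycles between day 15 and day 21". Section 7.1.4.4 agrees.

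**Analysis.** Section 3.2 names response duration and PFS among the secondary measures. Section 8.3 says "In general, data for continuous parameters will be presented using descriptive statistics including sample size, mean, and median; standard deviation". Section 8 does not define either measure, gives no censoring rule and names no time-to-event method.

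**The concern.** The narrative and the chart differ on three things at once: the interval (6 or 8 weeks), the patients (all who stop without progression, or only those with ongoing toxicity) and the content (imaging, or a visit with no imaging mark). They cannot all be followed.

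The patients in the gap are few but informative. Section 5.7.1 allows treatment to stop after a confirmed complete response, and Section 7.1.3 sends those patients on to the follow-up period. They contribute the longest response durations. Without ongoing toxicity, the chart leaves them with no scheduled scan. Whether progression is seen, and on what date, would then depend on why treatment stopped and on which part of the protocol the site used. Retreatment under Section 7.1.6.2 also requires confirmed radiographic progression after stopping, so the same gap reaches a decision within the trial.

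**Working it through.** No sample size, alpha or power in the plan depends on the imaging schedule, so there is no design figure to reproduce. The check compares the sections and then sizes the effect.

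**1. Sections side by side, for a patient who stops without progression**

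| Source | Who is followed | Interval | Imaging |
|---|---|---|---|
| 5.7 | All | Not stated; refers to Section 6 | Not stated |
| 6.1 flow chart | Only those with ongoing treatment-related toxicity | 8 weeks (visits) | No mark |
| 7.1.6 | All | 6 weeks, then 9 weeks after 1 year | Required |

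**2. Reading the chart**
- The footnotes are unlettered in the text as read from the PDF. Their order fits the superscripts: the first is on cycle length (a, on Treatment Cycles), the sixth on baseline imaging (f), the seventh on ECG (g) and the eighth on scans (h). The second is therefore b, the superscript on Follow Up Visits.
- The blank imaging cells look deliberate, because the serum chemistry row is marked in the Follow Up Visits column.

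**3. What the gap can do: a constructed example**
- Scheduled scans fall every 3 × 3 = 9 weeks, so at about weeks 9 and 18.
- Suppose a complete response is first seen at week 9, confirmed at week 18, and treatment stops at week 24, the minimum in Section 5.7.1.
- Under the chart, without toxicity, no further scan is scheduled. If the patient is censored at the last scan, response duration is 18 − 9 = 9 weeks, however long the response lasts.
- Under 7.1.6, scans continue every 6 weeks and progression can be dated.

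**4. What the interval alone can do**

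If progression falls evenly within a scan interval of L days, the mean lag to detection is L/2:
- 6-weekly: 42/2 = 21 days
- 8-weekly: 56/2 = 28 days
- 9-weekly: 63/2 = 31.5 days

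The difference between 9- and 6-weekly is 10.5 days (1.5 weeks). Between 8- and 6-weekly it is 7 days (1 week).

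A simulation gives similar figures. It assumes exponential residual time to progression with a median of 8 to 26 weeks (an assumption, since the documents give no PFS figure) and uses 1,000,000 draws per setting.

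| Scan interval | Mean lag (weeks) | Later than 6-weekly (weeks) |
|---|---|---|
| 6-weekly | 3.1–3.3 | – |
| 8-weekly | 4.1–4.5 | 1.1–1.2 |
| 9-weekly | 4.7–5.1 | 1.6–1.8 |

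Only patients who stop without progression are affected. If they are a share s of the cohort (not given; 10% to 50% shown), the shift in the cohort mean between 9- and 6-weekly is s × 1.5 weeks: 0.15 weeks at 10% and 0.75 weeks at 50%.

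**The case against.** The best defence is that the narrative governs. Section 7.1 describes the chart as a summary, with the detail in the text that follows, and 7.1.6 is that detail. Section 5.7 separately requires disease-status follow-up. On this view the chart merely lacks a mark. Part of the chart is also illegible in the extracted text. What stands is that loss of these patients to progression follow-up is a risk and not a certain result of the plan. The defence does not remove the conflict: 5.7 itself refers to Section 6 for the follow-up procedures, 7.1.4 does the same for visit requirements, and the rows and footnotes that matter are readable.

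Four stronger readings are tempting, and the documents support none of them.

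- **That 9-weekly scans on treatment contradict 7.1.6.** They cover a different phase and both can be followed. The only consequence is that scan frequency changes when treatment stops.
- **That PFS and response duration are biased.** They can be. Size and direction depend on which text sites follow, how many patients stop without progression, and an unstated censoring rule. The 1.5-week interval effect is close to the ± 7-day window that 7.1.6 allows.
- **That late entrants have only 2 months of follow-up (14 − 12).** This subtracts two estimated durations in the trial summary, which also gives 6 months of participation. It is not an established follow-up time.
- **That Section 8.3 plans a mean PFS ignoring censoring.** It speaks of continuous data in general and never says how PFS will be summarised. The supportable point is that no time-to-event method is named.

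**Conclusion.** The conflict is real and should be resolved. Its main consequence is that patients who stop without progression and without toxicity may have no scheduled scan, so their PFS and response duration may be censored at the last on-treatment scan or their progression dated late. The documents do not allow that loss to be quantified. The interval difference is secondary: about 1.5 weeks of mean detection lag between 6- and 9-weekly scans (1.6 to 1.8 weeks under the exponential assumption), in the affected patients only.

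The reach is limited. Both measures are secondary and preliminary, Section 8.3 rules out formal testing, and Section 8.1 plans no comparison between arms. The determination of the recommended phase 2 dose is not affected. The conclusion rests on reading the second footnote as b and on taking the blank imaging cells as intended.

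**What to change.** 1. Reconcile Sections 5.7, 6.1 and 7.1.6 to one stated post-treatment imaging schedule for every patient who stops without progression. The sponsor chooses the interval; the documents do not show that any one is right.
2. Mark Tumor Imaging in the flow chart's follow-up column, and detach footnote b from disease-status follow-up. It can stay on toxicity follow-up if that is what was meant.
3. Consider the same scan timing on and off treatment, so that progression dates do not depend on treatment status.
4. In Section 8, define PFS and response duration, state the censoring rule, and report both by Kaplan-Meier.

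The cost is mainly wording in the protocol and chart. Compared with the chart as it stands, the change adds scans for patients who stop without progression. Compared with 7.1.6, the number of scans depends on the interval chosen. Sample size and dose-finding rules do not change.

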#### **7.1.6.1 Survival Follow-up**

Once a subject experiences confirmed disease progression or starts a new anti-cancer therapy, the subject moves into the survival follow-up phase and should be contacted by telephone every 12 weeks to assess for survival status until death, withdrawal of consent, or the end of the study, whichever occurs first.

#### **7.1.6.2 Second Course Phase (Retreatment Period)**

Subjects who stop pembrolizumab/ XL888 with SD or better may be eligible for up to one year of additional pembrolizumab/ XL888 therapy if they progress after stopping study treatment. This retreatment is termed the Second Course Phase of this study and is only available if the study remains open and the subject meets the following conditions:

- **Either**
  - Stopped initial treatment with pembrolizumab/ XL888 after attaining an investigator-determined confirmed CR according to RECIST 1.1, and
    - Was treated for at least 24 weeks with pembrolizumab/ XL888 before discontinuing therapy
    - Received at least two treatments with pembrolizumab/ XL888 beyond the date when the initial CR was declared
- OR**
- Had SD, PR or CR and stopped pembrolizumab/ XL888 treatment after 24 months of study therapy for reasons other than disease progression or intolerability

**AND**

- Experienced an investigator-determined confirmed radiographic disease progression after stopping their initial treatment with pembrolizumab/ XL888
- Did not receive any anti-cancer treatment since the last dose of pembrolizumab/ XL888
- Has a performance status of 0 or 1 on the ECOG Performance Scale
- Demonstrates adequate organ function as detailed in Section 5.1.2
- Female subject of childbearing potential should have a negative serum or urine pregnancy test within 72 hours prior to receiving retreatment with study medication.
- Female subject of childbearing potential should be willing to use 2 methods of birth control or be surgically sterile, or abstain from heterosexual activity for the course of the study through 120 days after the last dose of study medication (Reference Section 5.7.2). Subjects of child bearing potential are those who have not been surgically sterilized or have been free from menses for > 1 year.
- Male subject should agree to use an adequate method of contraception starting with the first dose of study therapy through 120 days after the last dose of study therapy.
- Does not have a history or current evidence of any condition, therapy, or laboratory abnormality that might interfere with the subject's participation for the full duration of the trial or is not in the best interest of the subject to participate, in the opinion of the treating investigator.

Subjects who restart treatment will be retreated at the same dose and dose interval as when they last received pembrolizumab/ XL888. Treatment will be administered for up to one additional year.

Visit requirements are outlined in Section 6.0 – Trial Flow Chart.

## **7.2 Assessing and Recording Adverse Events**

An adverse event is defined as any untoward medical occurrence in a patient or clinical investigation subject administered a pharmaceutical product and which does not necessarily have to have a causal relationship with this treatment. An adverse event can therefore be any unfavorable and unintended sign (including an abnormal laboratory finding, for example), symptom, or disease temporally associated with the use of a medicinal product or protocol-specified procedure, whether or not considered related to the medicinal product or protocol-specified procedure. Any worsening (i.e., any clinically significant adverse change in

frequency and/or intensity) of a preexisting condition that is temporally associated with the use of the investigational products, is also an adverse event.

Changes resulting from normal growth and development that do not vary significantly in frequency or severity from expected levels are not to be considered adverse events. Examples of this may include, but are not limited to, teething, typical crying in infants and children and onset of menses or menopause occurring at a physiologically appropriate time.

Investigational products include pembrolizumab and XL888.

Adverse events may occur during the course of the use of investigational products in clinical trials, or as prescribed in clinical practice, from overdose (whether accidental or intentional), from abuse and from withdrawal.

All adverse events that occur after the consent form is signed but before treatment allocation/randomization must be reported by the investigator if they cause the subject to be excluded from the trial, or are the result of a protocol-specified intervention, including but not limited to washout or discontinuation of usual therapy, diet, placebo treatment or a procedure.

From the time of treatment allocation/randomization through 30 days following cessation of treatment, all adverse events must be reported by the investigator. Such events will be recorded at each examination on the Adverse Event case report forms/worksheets. The reporting timeframe for adverse events meeting any serious criteria is described in section 7.2.4. The investigator will make every attempt to follow all subjects with non-serious adverse events for outcome.

### **7.2.1 Definition of an Overdose for This Protocol and Reporting of Overdose to the Sponsor and to Merck/ Exelixis**

For purposes of this trial, an overdose of pembrolizumab will be defined as any dose of 1,000 mg or greater ( $\geq 5$  times the indicated dose). Overdose of XL888 is defined as  $\geq$  double the indicated dose. No specific information is available on the treatment of overdose of pembrolizumab. Appropriate supportive treatment should be provided if clinically indicated. In the event of overdose, the subject should be observed closely for signs of toxicity. Appropriate supportive treatment should be provided if clinically indicated.

If an adverse event(s) is associated with (“results from”) the overdose of an investigational product, the adverse event(s) is reported as a serious adverse event, even if no other seriousness criteria are met.

If a dose of investigational product meeting the protocol definition of overdose is taken without any associated clinical symptoms or abnormal laboratory results, the overdose is reported as a non-serious Event of Clinical Interest (ECI), using the terminology “accidental or intentional overdose without adverse effect.”

All reports of overdose with and without an adverse event must be reported within 24 hours to the Sponsor and within 2 working days to Merck Global Safety (Attn: Worldwide Product Safety; [contact]) and Exelixis ([contact]).

### 7.2.2 Reporting of Pregnancy and Lactation to the Sponsor and to Merck/ Exelixis

Although pregnancy and lactation are not considered adverse events, it is the responsibility of investigators or their designees to report any pregnancy or lactation in a subject (spontaneously reported to them) that occurs during the trial.

Pregnancies and lactations that occur after the consent form is signed but before treatment allocation/randomization must be reported by the investigator if they cause the subject to be excluded from the trial, or are the result of a protocol-specified intervention, including but not limited to washout or discontinuation of usual therapy, diet, placebo treatment or a procedure.

Pregnancies and lactations that occur from the time of treatment allocation/randomization through 120 days following cessation of investigational products, or 30 days following cessation of treatment if the subject initiates new anticancer therapy, whichever is earlier, must be reported by the investigator. All reported pregnancies must be followed to the completion/termination of the pregnancy. Pregnancy outcomes of spontaneous abortion, missed abortion, benign hydatidiform mole, blighted ovum, fetal death, intrauterine death, miscarriage and stillbirth must be reported as serious events (Important Medical Events). If the pregnancy continues to term, the outcome (health of infant) must also be reported.

Such events must be reported within 24 hours to the Sponsor and within 2 working days to Exelixis ([contact]) and Merck Global Safety. (Attn: Worldwide Product Safety; [contact])

### 7.2.3 Serious Adverse Events

A serious adverse event is any adverse event occurring at any dose or during any use of investigational product that:

- Results in death;
- Is life threatening;
- Results in persistent or significant disability/incapacity;
- Results in or prolongs an existing inpatient hospitalization;
- Is a congenital anomaly/birth defect;
- Is another important medical event
- **Note:** In addition to the above criteria, adverse events meeting either of the below criteria, although not serious per ICH definition, are reportable to the Merck and Exelixis in the same timeframe as SAEs to meet certain local requirements. Therefore, these events are considered serious by Merck/ Exelixis for collection purposes.
  - Is a new cancer (that is not a condition of the study);

- Is associated with an overdose.

Refer to Table 6 for additional details regarding each of the above criteria.

For the time period beginning when the consent form is signed until treatment allocation/randomization, any serious adverse event, or follow up to a serious adverse event, including death due to any cause that occurs to any subject must be reported within 24 hours to Sponsor and within 2 working days to Merck Global Safety and Exelixis if it causes the subject to be excluded from the trial, or is the result of a protocol-specified intervention, including but not limited to washout or discontinuation of usual therapy, diet, placebo treatment or a procedure.

For the time period beginning at treatment allocation/randomization through 90 days following cessation of treatment, or 30 days following cessation of treatment if the subject initiates new anticancer therapy, whichever is earlier, any serious adverse event, or follow up to a serious adverse event, including death due to any cause whether or not related to the Exelixis and Merck product, must be reported within 24 hours to sponsor and within 2 working days to Exelixis and Merck Global Safety.

Serious adverse events related to study treatment or study procedures must be recorded even if the SAE occurs more than 30 days after cessation of treatment and also must be reported immediately to the Sponsor and to Exelixis and Merck Global Safety.

All subjects with serious adverse events must be followed up for outcome.

